## 1.4 Sample Size Estimates

The planned sample size for each pairwise comparison is 1,000 participants (500 participants in each group). The sample size is sufficient to detect a recovery rate ratio (RRR) of 1.25 for time to sustained recovery with 90% power, using a one-sided test with a significance level of 0.025. The treatment groups are compared using Gray’s test with  $\rho=0$ , the competing risks analogue of the log-rank test.

Sample size calculations are described in detail in Section 6.3 of the protocol.

Blinded sample size re-estimation will be carried out before enrollment is complete to determine whether the planned sample size of 1,000 participants followed for 90 days will yield the planned number of 843 primary events. The blinded sample size re-estimation does not involve unblinding of the treatment difference. It will be based on the pooled outcome data. Sample size may be increased to achieve the event target in the planned follow-up of 90 days. A

sample size increase may also be considered in order to achieve the event target before all participants are followed for 90 days.

When 300 participants (150 per study arm) are enrolled and have Day 5 outcome data, an early futility assessment is planned. This assessment will be based on two ordinal outcomes, denoted as “pulmonary” and the “pulmonary+”; both are ordered categorical outcomes with 7 categories, assessed on Day 5 (the two outcomes are described in [Appendix A](#)). Treatment groups will be compared using proportional odds models. With 300 participants, the early futility assessment is powered to detect a summary OR=1.60 with power of 95%, using a one-sided test with significance level of 0.30. Given the two-outcome decision rules, an investigational agent with a summary OR=1.60 at Day 5 for both outcomes, would pass the futility assessment with a power between 93% and 98%, and a type I error between 0.21 and 0.39.

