### Censoring for time-to-event analyses

For **interim** analyses, the type of censoring used will depend on the data collection schedule.

- If the reporting of the endpoint is data-driven (e.g., SAEs and deaths are reported as they occur), then follow-up is censored at the administrative censoring date, at the date of withdrawal, or loss to follow-up, whichever occurs earliest.
- If the date of the event is elicited retrospectively at fixed study visits spaced more than one week apart (e.g., “sustained recovery”), follow-up will be censored at the last day the endpoint status was ascertained.
- Sensitivity analyses will be provided for key analyses when the outcome status is uncertain.

For **final** analyses, follow-up will be censored on the last day the outcome status was ascertained.

**Adverse events** (AEs) will be classified by system organ class according to MedDRA® (currently version 24.1 [September 2021] is used; when new versions are implemented, items are recoded). AEs will be graded according to the *DAIDS Table for Grading the Severity of Adult and Pediatric Adverse Events, Corrected Version 2.1* (July 2017) (also referred to as the *DAIDS AE Grading Table*). Cause of death will also be coded according to MedDRA®.

The number and percent of participants with grade 1-4 AEs will be summarized by day and grade, and by MedDRA® System Organ Class and grade. The percentage of participants with AEs will be compared between treatment groups according to grade cut-offs, e.g., “percent of participants with any AE”, “percent of participants with grade 2 or higher AEs”, etc., using CMH tests. The total number of events and median (IQR) of events per participant will also be summarized.

Additionally, the incidence of grade 3 and higher AEs will be summarized (number and percent of participants), and compared between treatment groups using time-to-event methods.

**Significance level, two-sided tests:** Unless noted otherwise, statistical tests and confidence intervals will be 2-sided, confidence intervals will have approximate 95% coverage probability, and test results with P-values  $\leq 0.05$  will be considered “significant”. Percentages will be reported to at least one decimal place. P-values will be given to 2 significant figures.

**Cut-date for interim reviews:** Analysis data sets will be frozen (locked) several days (or weeks) prior to the review date, to allow the unblinded statisticians time to prepare a consistent

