- AEs, SAEs, and UPs will be classified by MedDRA® system organ class. AEs will be graded for severity according to the *DAIDS AE Grading Table*. Grade 1-4 clinical AEs will be reported at baseline (Day 0 prior to infusion of the investigational agent), Day 0 after the infusion, Days 1-7, and on Days 14 and 28.

The number and percent of participants with AEs will be summarized by day (Day 0 separately prior and after the infusion) and grade, and by system organ class and grade. Comparisons between treatment groups will be for the proportion of participants with AEs of a given grade or higher (i.e., any grade, grade 2+, grade 3+, grade 4). The treatment comparisons will be performed using stratified CMH tests or logistic regression.

- For comparisons by day, the proportion of participants with any grade AEs will be compared for Days 0 (after infusion) through 7, and on Days 14 and 28.
- For comparisons by grade, the proportion of participants who experienced any grade AEs (grade 2+ AEs, etc.) between Day 0 (after the infusion) through Day 7 will be compared.
- For the comparison by system organ class, CMH tests will be performed if the number of participants with AEs is sufficiently large. System organ classes may be split up into MedDRA® preferred terms (PT) for system organ classes where the treatment difference is significant.

Other clinically meaningful AE groupings (beyond system organ class) may be developed by the study team, who are blinded to the treatment effect.

- In addition to any grade AEs through Day 7, grade 3 and 4 clinical AEs are being reported through Day 28. The number and percent of participants with incident grade 3 or 4 AEs through Day 28 will be summarized, overall and by system organ class, and compared between treatment groups using stratified CMH tests. (A grade 3 or 4 AE is considered “incident” if the event was not present at baseline or increased to grade 3 or 4 from grades 1 or 2.)

To illustrate the time course, the incidence of *grade 3 or 4 AEs or death* through Day 28 will be summarized by treatment group using Kaplan-Meier estimates of the cumulative incidence functions (CIF).

- Infusion-related reactions and symptoms during infusion or within 2 hours after infusion of the investigational agent or placebo, and infusion cessation prior to completion will be tabulated and compared between treatment groups; analyses are described in section 6.

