### E-3 Power Estimation Prior to Unblinding

On December 28, 2021, prior to unblinding any treatment comparisons for the trial of AZD7442, power was re-assessed based on updated pooled (AZD7442 and placebo groups combined) primary endpoint results. Pooled primary outcome data on December 28, 2021 are given in the table below.

**Table E-1.** Recovery status of participants in the AZD7442 trial as of December 28, 2021

	1455 Participants Randomized				
	1417 Infused and 38 not infused (35 withdrew consent)				
	nAb negative	nAb positive	Specimen not yet analyzed	Specimen not available	TOTAL
Recovery status through Day 90	N=616	N=657	N=107	N=37	N=1417
Withdrew prior to recovery	2	4	0	0	6
Day 90 window closed and recovery status unknown	17	5	0	1	23
Day 90 window not yet closed* and recovery status unknown	0	1	3	0	4
Achieved sustained recovery	508	586	76	25	1195
Home < 14 days	7	5	0	0	12
Discharged from hospital, but not home	9	3	0	2	14
Hospitalized	12	10	2	1	25
Died before recovery	61	43	26	8	138

\* The Day 90 window extends to Day 100.

The mITT study population included 1417 participants. At this time, most of the 90-day follow-up was completed. The last patient was randomized on September 30, 2021 and the visit window for the Day 90 visit extends to 100 days (January 8, 2022).

Overall, the number of primary events was 1,195, 33 events less than the target of 1,228. As the table below indicates, this does not have a material effect on power.

**Table E-2.** Power estimates in the full study population: Recovery rate ratios (RRR) that can be detected with 80-90% power and 0.05 (2-sided) significance level, assuming 1195 sustained recovery events pooled across treatment groups

Power	RRR
0.90	1.206
0.85	1.189
0.80	1.176

**Table E-3** below summarizes power estimates for the subgroup of participants who were nAb-negative at study entry. This subgroup is currently 48% of those for whom the baseline nAb status was determined. We anticipate results for 107 additional patients in January 2022. The effect sizes (recovery rate ratio [RRR]) that can be detected with 90%, 85%, and 80% power for different estimates of the final number of primary events for the nAb-negative subgroup are summarized below; as of December 28, 2021, 508 participants in this subgroup had achieved sustained recovery, and 76 participants among those for whom the nAb status is not yet known.

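### The only stated route to adverse-event preferred terms by arm is optional and depends on a significant organ-class test, which can miss a rise in a single term

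*SAP*

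**What the plan says.** The adverse-event paragraph of SAP section 3 sets the level of the routine summary: "The number and percent of participants with grade 1-4 AEs will be summarized by day and grade, and by MedDRA® System Organ Class and grade". SAP section 7 repeats this level and adds the class comparison, under which "CMH tests will be performed if the number of participants with AEs is sufficiently large". It then gives its one sentence on preferred terms, which says that classes may be divided into them "for system organ classes where the treatment difference is significant".

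Significance here takes the SAP's general meaning. Unless noted otherwise, "statistical tests and confidence intervals will be 2-sided", with a p-value threshold of 0.05 (SAP section 3). No other section of the supplied documents commits to a table of preferred terms by arm.

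The sentence after the preferred-term rule in section 7 lets the study team, blind to the treatment effect, develop other clinically meaningful AE groupings.

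**The concern.** The breakdown that would show a specific reaction is reached through a test on a pooled category. The rule is permissive: a significant class need not be split, and for a non-significant class no preferred-term display is stated. A class too sparse to be tested cannot trigger the rule at all.

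Dilution is the mechanism. Unrelated events in the class raise the rate in both arms, which shrinks the relative contrast and inflates the variance of the class difference. The SAP's own platform data show something similar in another setting. Pooled over the first three agents, the Day 90 safety composite was 25.3% against 27.2% (HR 0.95; section 9.2). Yet new dialysis, one component of organ failure, occurred 18 times against 2 (HR 5.7, 95% CI 1.2 to 24.6; section 7). The SAP notes that two of the active-arm dialysis cases may be misclassified, and a composite is not an organ class. Still, section 7 compares organ-failure components whatever the overall result, and ordinary AEs do not get the same treatment.

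At stake is whether a moderate rise in one lower-grade reaction appears as a count by arm in the planned tables.

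**Working it through.** The documents attach no figure to this rule, so there is no plan figure to reproduce. The check asks how often the class test would be non-significant when one term truly differs.

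**Inputs from the documents**
- Two-sided 0.05 (SAP section 3).
- 500 per arm (SAP section 1.4).
- For AZD7442, "The mITT study population included 1417 participants" (Appendix E-3), so about 1417/2 ≈ 708 per arm if evenly split.
- For MP0420, 485 infused (Appendix G), so about 242 per arm.

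**Assumed inputs (the documents give no class or term rates)**
- Term rate t: 1% on control, 4% on active.
- Other events in the class, b: 2% to 30%, equal in both arms and independent of the term.
- Unstratified comparison of two proportions.

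**Formulas**
- Class rate: p = 1 − (1 − b)(1 − t).
- Power: Φ[(d − 1.96·SE0)/SE1], where d = p2 − p1, SE0 = √(2·p̄(1 − p̄)/n) and SE1 = √((p1(1 − p1) + p2(1 − p2))/n).
- Chance that the class is non-significant: 1 − power.

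**Term compared directly, n = 500.** d = 0.03, SE0 = 0.00987, SE1 = 0.00983. Power = Φ[(0.03 − 0.01935)/0.00983] = Φ(1.083) = 86%, so it is non-significant with probability 14%.

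**Class with b = 5%, n = 500.** p1 = 1 − 0.95 × 0.99 = 0.0595 and p2 = 1 − 0.95 × 0.96 = 0.0880, so d = 0.0285. SE0 = 0.01653 and SE1 = 0.01651. Power = Φ[(0.0285 − 0.03240)/0.01651] = Φ(−0.236) = 41%, so it is non-significant with probability 59%.

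**All backgrounds, term 1% vs 4%, n = 500.** The last column comes from a simulation of 40,000 runs per scenario. It counts only runs in which the term difference was itself significant.

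| Background b | Class rate, control | Class rate, active | Class power | Class non-significant | Class non-significant, given term significant |
|---|---|---|---|---|---|
| 2% | 2.98% | 5.92% | 62% | 38% | 31% |
| 5% | 5.95% | 8.80% | 41% | 59% | 55% |
| 10% | 10.90% | 13.60% | 26% | 74% | 72% |
| 20% | 20.80% | 23.20% | 15% | 85% | 84% |
| 30% | 30.70% | 32.80% | 11% | 89% | 88% |

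**Sensitivity**
- About 708 per arm, 1% vs 4%: class non-significant with probability 23% at b = 2% and 46% at b = 5%. Term power is 95%.
- 242 per arm, 1% vs 4%: class power is 22% at b = 5% and 7% at b = 30%. Term power is only 56%, so part of the loss there is ordinary low power.
- 500 per arm, 1% vs 3%: class power is 22% at b = 5% and 7% at b = 30%. Term power is 62%.
- 36 scenarios at 500 per arm (term 1% vs 3-5% or 2% vs 4-6%; b from 2% to 30%): the chance that the class is non-significant runs from 18% to 93%.

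**The case against.** The strongest reply is that the plan neither forbids a wider breakdown nor relies on this rule to find harm.

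- **Wording.** The text says classes may be split where the difference is significant. It does not say only there, and it allows other blinded groupings. This stands, but neither permission commits anyone to a by-arm display of terms.
- **Other routes.** Listings by treatment group at each DSMB meeting cover SAEs, incident grade 3-4 AEs, organ failure and serious infections, unanticipated problems, SUSARs and deaths (section 7). Organ failure and serious infections are compared by component (section 7). Infusion reactions are tabulated by grade (section 6). All of this is independent of class significance, and it stands. What remains is narrower: listings are not counts by term and arm, infusion reactions are captured only to two hours after the infusion, and later grade 1-2 events have no term-level display.
- **Background.** Appendix C keeps many COVID-19 complications, such as respiratory failure, thromboembolism, delirium and serious infection, out of AE reporting unless considered related. This stands as a reason to look at the low-background rows as well as the high ones.
- **MP0420.** Appendix G tabulates rash by arm with no class-level trigger. That shows the team can act outside the rule, but the prompt was hypersensitivity reactions reported from another study.

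A reader might also infer that the SAP treats a non-significant class as cleared. It draws no such conclusion. Nor is the chance of a false trigger a strong point. It would be 1 − 0.95^14 = 51% for 14 independent class tests, but the number of classes is assumed, sparse classes are not tested, and a trigger only permits a breakdown.

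**Conclusion.** The point holds in a limited form. In the supplied documents the only stated route to preferred terms by arm is optional and depends on a class-level test that dilution can weaken badly. For a term rising from 1% to 4% with 500 per arm, the class test is non-significant with probability about 38%, 59% and 89% at backgrounds of 2%, 5% and 30%, against 14% for the term itself. This rests on assumed term and class rates, independence within the class and an unstratified test. At about 708 per arm and 2% background the figure is 23%.

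Two stronger readings are tempting. One is that real harms would stay hidden some fixed large share of the time. The documents give no rates from which to derive such a share, and the scenarios tried span 18% to 93%. The other is that serious or unexpected reactions would go unseen. They are listed or tabulated regardless of class significance. The gap is by-arm preferred-term counts, chiefly for grade 1-2 AEs.

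**What to change.** In SAP section 7, replace the sentence on splitting classes with:

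> Within every system organ class, preferred terms will be tabulated by treatment group (number, percent, risk difference with 95% CI), descriptively and regardless of the class-level p-value.

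Add a display threshold, such as at least 1% in either arm, to keep the table short.

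The cost is one extra standard table; section 3 already has AEs classified with MedDRA. The primary analysis, the sample size and its type I error are unaffected. The downside is a set of unadjusted intervals, some of which will exclude zero by chance, so the table should be labelled descriptive.

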## 7 Safety Analyses

The planned timing of safety reviews is described in section 2. An overview of the safety data collection is provided in [Appendix C](#).

**Analysis cohort:** Safety analyses will be carried out on participants who received a complete or partial infusion of the investigational agent (modified intention-to-treat [mITT]), unless otherwise stated.

A comprehensive safety review includes:

- Comparison of the treatment groups for the primary safety endpoint, its components, and analyses of secondary safety outcomes (described in this section)
- Analyses of infusion-related reactions and symptoms, described in section 6
- Evaluation of the “efficacy outcomes” (the pulmonary and pulmonary+ ordinal outcomes early in follow-up, and time to sustained recovery), which contain important safety information.

In addition to the full DSMB reviews, more frequent, shorter safety reports may be provided to the DSMB, for example, weekly safety reports early in the trial.

This section describes the primary safety outcome, and the analyses of AEs, SAEs, UPs, SUSARs, and deaths. Comparisons between treatment groups will be stratified by study pharmacy and by disease severity at study entry (as described in section 3 under “stratification”).

In order to streamline the reporting of events, it was decided that certain protocol-specified exempt events (PSEE) are *not reported as SAEs*, unless they are considered related to the study treatment by the investigator. The events are listed in [Appendix B](#); their composite is referred to as *clinical organ failure or serious infections*. While the *clinical organ failure or serious infection* events are serious events like SAEs, these events are reported not on the SAE eCRF unless they are considered related to the study treatment, but are reported as study endpoints on various other eCRFs.

The following safety and tolerability outcomes will be analyzed. If sample size permits, models will be stratified by disease severity and study site pharmacy, as described in section 3 under “stratification”, unless noted otherwise.

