- The **primary safety endpoint** is a composite of incident grade 3 or 4 clinical adverse events, SAEs, clinical organ failure or serious infections, or death through **Day 5**. The number and proportion of participants experiencing one of these events up through Day 5 will be tabulated, and treatment groups will be compared using a CMH test stratified by study site pharmacy and by disease severity at study entry.
  - Mortality will be analyzed as a key secondary outcome, see below.
  - The individual components of the composite outcome will be summarized.
  - *Sensitivity analyses*: For interim analyses, while the trial is still enrolling, treatment groups will also be compared for time to event through Day 5 using a log-rank test, stratified by site pharmacy and disease severity at study entry; the HR will be estimated with a 95% CI using a Cox proportional hazards model, and the cumulative proportion of participants with events over the first 5 days in each treatment group will be estimated using Kaplan-Meier curves.

**Comment:** For investigational agents that are administered as a one-time infusion, such as nMAbs, the composite outcome at Day 5 is the primary measure to assess safety while the trial is still enrolling, as described in the protocol. This safety outcome and other safety outcomes through Day 28 will be considered along with the ordinal outcomes at Day 5 at interim data reviews by the DSMB to assess futility. When a trial is unblinded after the Day 90 follow-up is completed, however, treatment comparisons through Day 90 provide a more comprehensive evaluation of the investigational agent. For the publication of the main results for a specific agent, “time to death” and the composite of “death, SAE, clinical organ failure, or serious infections” through Day 90 would usually be presented as the main safety analyses, along with other safety outcomes. This decision will be agent-specific, and will be specified prior to the unblinding of the data for the agent.

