**Comment:** Of the 20 participants with “incident dialysis”, 2 had required dialysis prior to their COVID-19, and thus may be mis-classified for treatment-emergent dialysis. Both had eGFR < 10 mL/min at study entry and thus were at high risk for dialysis, and both had been allocated to active treatment.

**Hypothesis:** The incidence of dialysis is elevated with nMAb treatment compared with placebo, in particular among those with eGFR < 30 mL/min, and among those who are nAb seronegative at study entry.

- Treatment groups will be compared for mean changes in laboratory test values from baseline to Day 5, and for incidence of grade 3 and 4 laboratory abnormalities at Day 5 (new abnormality or increase in grade). Laboratory tests are conducted locally, and include serum creatinine, AST/SGOT or ALT/SGPT, WBC, hemoglobin, platelet counts, lymphocyte counts, and C-reactive protein. Statistical methods are described in section 3.
- Participants who are pregnant are not eligible for enrolment. For participants who become pregnant, pregnancy outcomes will be summarized.
- In addition to the safety outcomes specified in the platform protocol, other targeted safety outcomes for specific investigational agents may be specified in appendices to the protocol. Analyses will be specified in the corresponding agent-specific appendix to this SAP.

Listings of SAEs, clinical organ failure and serious infections, incident grade 3 and 4 AEs, UPs, SUSARs, and deaths (with cause of death) by treatment group will be provided at each DSMB meeting, with new events highlighted. The listings will include important baseline characteristics, such as age, sex, and disease severity (pulmonary outcome category) at study entry.

Further safety assessments may be considered.

Corticosteroid use will be monitored; concomitant medication use is collected at baseline and at Day 5.

- Corticosteroid use (any use at baseline or Day 5) will be summarized by treatment group and by oxygen requirement (worst category through Day 5: no supplemental oxygen, < 4 L/min, conventional supplemental oxygen  $\geq$  4 L/min, high-flow oxygen or mechanical ventilation/ECMO).
- Corticosteroid use on Day 5 will be summarized by treatment group and by oxygen requirement (worst category on Day 5, as above).

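### The definition of an incident grade 3 or 4 clinical AE leaves out worsening from baseline grade 3 to grade 4, so the outputs built on it can miss such events

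*SAP*

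**What the plan says.** All of the following is in SAP section 7 unless noted.

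- **Clinical rule.** In the bullet on grade 3 and 4 clinical AEs through Day 28, an event is incident if "the event was not present at baseline or increased to grade 3 or 4 from grades 1 or 2". The bullet governs a stand-alone comparison: "The number and percent of participants with incident grade 3 or 4 AEs through Day 28 will be summarized, overall and by system organ class". The SAP gives no other definition of the term for clinical AEs.
- **Primary safety endpoint (Day 5).** This "is a composite of incident grade 3 or 4 clinical adverse events, SAEs, clinical organ failure or serious infections, or death through" Day 5. The Day 28 composite uses the same term.
- **Baseline grades.** "Grade 1-4 clinical AEs will be reported at baseline (Day 0 prior to infusion of the investigational agent"). A grade 3 event at entry can therefore be recorded, and its grade is known.
- **Laboratory rule.** Arms are compared for "incidence of grade 3 and 4 laboratory abnormalities at Day 5 (new abnormality or increase in grade").
- **By-grade comparison.** Arms are also compared for the proportion with AEs "of a given grade or higher (i.e., any grade, grade 2+, grade 3+, grade 4"). The window runs from Day 0 after infusion through Day 7, and the text does not restrict it to incident events.
- **Listings.** Section 7 and section 10.1 restrict the grade 3 and 4 AE listing to incident events. The closed-report list in section 2 does not.

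**The concern.** A safety endpoint should count a severe event that becomes potentially life-threatening after infusion. Read literally, the clinical rule does not. The event was already there at baseline, and it did not rise from grade 1 or 2. The laboratory rule would count the same step, and the SAP gives no reason for the narrower clinical rule.

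The population makes the case possible. Participants are inpatients with COVID-19, and Appendix E-5 records that eligibility for AZD7442 was later widened to patients on high-flow oxygen or non-invasive ventilation.

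The term also reaches outputs that matter. Section 7 describes the Day 5 composite as the main safety measure for single-infusion agents while enrolment continues. If an agent made existing severe symptoms worse, part of that signal could drop out of the AE component. An omission that falls equally on both arms only removes events. A difference between arms in the rate of worsening from grade 3 to 4 would be understated.

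**Working it through.** The documents give no event rate, power or sample size for the safety composite, so there is no figure to reproduce. The check has two parts.

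**1. Which transitions does the wording affect?** Let *b* be the baseline grade (0 = absent) and *f* the worst grade after infusion.

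- SAP clinical rule: incident if *f* ≥ 3 and *b* is 0, 1 or 2.
- Laboratory-type rule: incident if *f* ≥ 3 and *f* > *b*.

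| Baseline → follow-up | SAP clinical rule | Any increase in grade |
|---|---|---|
| 0→3, 0→4 | incident | incident |
| 1→3, 1→4 | incident | incident |
| 2→3, 2→4 | incident | incident |
| 3→3 | not incident | not incident |
| **3→4** | **not incident** | **incident** |
| 4→3, 4→4 | not incident | not incident |

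The two rules differ on one transition only.

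**2. How many participants could a composite miss?** A participant is missed only if the 3→4 event is not also an SAE, organ failure, serious infection or death, and no other qualifying event occurs in the window. Over the Day 5 window:

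missed = N × q × r × (1 − c)

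- N = 300 (early futility review) or 1,000 (planned total per comparison), from SAP sections 1.2 and 1.4, both arms together.
- q = share with a grade 3 clinical AE at baseline. Not in the documents; assumed 2% to 20%.
- r = share of those reaching grade 4 by Day 5. Not in the documents; assumed 5% to 20%.
- c = share of those already counted through another component or event. Not in the documents; 0 to 1.

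| q, r | c | N = 300 | N = 1,000 |
|---|---|---|---|
| 2%, 5% | 0 | 300 × 0.02 × 0.05 = 0.3 | 1.0 |
| 5%, 10% | 0 | 300 × 0.05 × 0.10 = 1.5 | 5.0 |
| 5%, 10% | 0.8 | 1.5 × 0.2 = 0.3 | 1.0 |
| 20%, 20% | 0 | 300 × 0.20 × 0.20 = 12 | 40 |
| any | 1 | 0 | 0 |

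The last 20% row is the extreme corner of the assumed ranges, with no overlap at all. The result depends heavily on c, and the documents do not allow c to be estimated. The SAE definition that would inform it is in the master protocol, which is not among the documents.

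**The case against.** The strongest reply is that little is actually lost.

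- **Other components of the composite.** SAEs, organ failure, serious infection and death enter without reference to the AE grade rule. Organ failure and serious infection "but are reported as study endpoints on various other eCRFs". Appendix B includes respiratory failure, hypotension needing vasopressors, new renal replacement, hepatic decompensation and delirium. Many worsenings to grade 4 would be counted this way. This stands. Complete capture cannot be shown, however, because the AE component is there to add events outside those categories.
- **The grade 4 cut-off.** A participant who goes from grade 3 to grade 4 after infusion is counted there, and the window covers the whole Day 5 period. This also stands. But the by-grade comparison stops at Day 7, nothing says it removes grade 4 events already present at entry, and it does not put the event back into either composite or the Day 28 incident comparison.
- **Listings.** The closed-report list in section 2 is unrestricted, so the DSMB may still see the case. Sections 7 and 10.1 say otherwise, so the text needs aligning.
- **Main published analyses.** Section 7 says these would usually be death, and death with SAEs, organ failure or serious infection, through Day 90. Neither uses the grade rule.
- **Where the definition sits.** It is in the Day 28 bullet. Carrying it over to the Day 5 composite is a reasonable inference from the shared term, not explicit text.
- **A kinder reading.** One could say that a grade 4 event was not present at baseline if only grade 3 was recorded. But then a rise from grade 1 or 2 would already qualify under the first condition, and the second would be redundant. If both readings are open, two programmers could code the rule differently.

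A reader might infer that the primary safety composite loses these deteriorations outright, that the grade 3 and 4 AE analyses have no backstop, or that a harmful agent would look safe. The documents do not support this. The gap lies in one component, the Day 7 comparison at grade 4 is a partial backstop, and section 7 makes the pulmonary and pulmonary+ outcomes part of every comprehensive safety review.

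**Conclusion.** The definition is wrong as worded: it leaves out worsening from baseline grade 3 to grade 4 and is inconsistent with the laboratory rule in the same section. The incident-AE component of the Day 5 and Day 28 composites, the stand-alone Day 28 comparison and the incident-only listings can therefore miss such an event when nothing else captures it.

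The omission itself follows from the text. Its size does not, since q, r and c are all assumed. At 5% and 10% the range is 0 to 1.5 per 300, or 0 to 5 per 1,000. The number is probably small and is zero if overlap is complete. The extension to the Day 5 composite rests on the shared term. This is a minor correction to a safety definition, worth making because the omitted step is a worsening to the top severity grade for a non-fatal event.

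**What to change.** Replace the parenthesis in SAP section 7 with wording such as: *a grade 3 or 4 AE is incident if it was absent at baseline, or if its grade rose from baseline to grade 3 or 4, including from grade 3 to grade 4.* State that the definition applies to the Day 5 and Day 28 composites, the stand-alone Day 28 comparison and the AE listings. Use the same description of the listing in sections 2, 7 and 10.1.

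The cost is one sentence and a small change to the derivation code. Baseline and follow-up grades are already collected, and sample size and alpha are unaffected. Make the change before the data for an agent are unblinded, in the SAP update that section 1.1 already foresees at that point.
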